### **5.10.3. Sensitivity Analyses**

The sensitivity analyses described in [Section 5.9.3](#) for the primary estimand will also be performed for the key secondary efficacy estimand.

### **5.10.4. Subgroup Analyses**

The subgroup analyses described in [Section 5.9.4](#) for the primary estimand will also be performed for the key secondary efficacy estimand and secondary endpoints.

## 5.11. Summary of Primary and Key Secondary Efficacy Analyses

ICE Strategy	Primary Analysis	Sensitivity Analysis	Subgroup Analysis
Primary Endpoint: Change from Baseline to Week 6 in the PANSS total score			
Hypothetical strategy with data after treatment discontinuations or after the start of prohibited concomitant medications censored	
 
• mITT population
 
• Treatment as randomized
 
• MMRM described in Section 5.9.2
 
	
 
• Treatment effect based on actual treatment received, if applicable
 
• Missing values imputation using multiple imputations (MI)
 
• Missing values imputation using pattern mixture model (PMM)
 
• Endpoint completer analysis
 
	
 
• Age
 
• Sex
 
• Baseline PANNS Total Score
 
• Baseline CGI-S
 
• Race
 
• Region
 

Key Secondary Endpoint: Change from Baseline to Week 6 in the CGI-S score			
Hypothetical strategy with data after treatment discontinuations or after the start of prohibited concomitant medications censored	
 
• mITT population
 
• Treatment as randomized
 
• MMRM described in Section 5.9.2
 
	
 
• Treatment effect based on actual treatment received, if applicable
 
• Missing values imputation using multiple imputations (MI)
 
• Missing values imputation using pattern mixture model (PMM)
 
• Endpoint completer analysis
 
	
 
• Age
 
• Sex
 
• Baseline PANNS Total Score
 
• Baseline CGI-S
 
• Race
 
• Region
 

## 5.12. Other Secondary Efficacy Analyses

### 5.12.1. Change From Baseline at All Time Points In PANSS Total Score

The MMRM analysis described in [Section 5.9.2](#) will also be the basis for evaluating the change from baseline at all time points.

### 5.12.2. Change From Baseline at All Time Points In CGI-S Score

The MMRM analysis described in [Section 5.9.2](#) will also be the basis for evaluating the change from baseline at all time points.

### 5.12.3. Percentage of PANSS Responders at Week 6/Early Termination Visit

The binary outcome will be defined as having at least 30% reduction from baseline or not having a 30% reduction at Week 6 or the early termination visit. If a subject discontinues and does not have an early termination visit, the subject's last assessment will be used. Subjects who do not achieve a 30% reduction will be considered a non-responder.

A logistic regression model, with baseline PANSS and geographic region as a covariate, will be used to compare the proportion of responders in each active arm with placebo. Odd ratios will be constructed for each emraclidine treatment dose group compared with placebo and will be summarized with a 95% confidence interval. If expected counts are  $<5$ , then a Fisher's Exact test will be used.

Similarly, the analysis will be repeated by the subgroups defined in [Section 5.9.4](#).

## 5.13. Summary of Analyses of Other Efficacy and Exploratory Endpoints

Endpoint	Analysis Population	Analysis Method
CGI-I at Weeks 3 and 6	mITT	MMRM described in Section 5.9.2 .
Change from Baseline at all time points in PANSS positive, negative, and general psychopathology subscale scores	mITT	MMRM described in Section 5.9.2 .
Change from Baseline at all time points in PANSS Marder Factor scores	mITT	MMRM described in Section 5.9.2 .
Change from Baseline at all time points in PANSS delusions and hallucinatory behavior scores	mITT	MMRM described in Section 5.9.2 .
Percentage of CGI-S responders ( $\geq$ 1-point improvement) at Week 6/ET visit	mITT	Logistic regression described in Section 5.12.3
Percentage of CGI-S responders ( $\geq$ 2-point improvement) at Week 6/ET visit	mITT	Logistic regression described in Section 5.12.3
Change from Baseline at Week 6 in BACS symbol coding test	mITT	MMRM described in Section 5.9.2 .
Change from Baseline at Week 6 in SF-6D	mITT	MMRM described in Section 5.9.2 .

## 5.14. Interim and Final Analysis

No interim analysis is planned.

A final analysis will be conducted once the last subject completes or discontinues the study, and the resulting clinical database has been cleaned, quality checked, the pre-analysis meeting has occurred, and the database has been locked.

## 5.15. Safety Analyses

All safety analyses will be performed on the FAS population. Should any subjects receive a treatment other than their randomized treatment, the treatment as received will be used in the safety presentation.

### 5.15.1. Adverse Events

Adverse events will be mapped to MedDRA version 26.0 or higher preferred term and system organ class. If a subject experiences multiple events that map to a single preferred term, the greatest severity and strongest investigator assessment of relation to IMP will be assigned to the preferred term for the appropriate summaries. Events with missing severity or relationship will be classified as outlined in [Section 3.2.1](#). Summaries of treatment-emergent AEs will include any AEs reported beginning with the initiation of study drug on Day 1 through the follow up contact. An overall summary of TEAEs, including the number of subjects with a TEAE, TEAE related to IMP, AESI, serious TEAE, serious TEAE related to IMP, TEAE leading to discontinuation of

IMP, and TEAE leading to death will be summarized. [REDACTED]

[REDACTED] The occurrence of treatment emergent adverse events (TEAEs) will be summarized by treatment group using preferred terms, system organ classes, and severity. Separate summaries of TEAEs, treatment-emergent serious adverse events (TESAEs), TEAEs related to IMP, AESIs, events leading to discontinuation of IMP will be generated by system organ class and preferred term.

Treatment-emergent adverse events with  $\geq 2\%$  incidence in either one of the emraclidine arms and a greater incidence than the placebo arm will be summarized by preferred term. The most common TEAEs in either one of the emraclidine arms, defined as an incidence  $\geq 5\%$  and greater than 2 times of the incidence in the placebo group, will also be summarized by treatment group using preferred term. [REDACTED] All

adverse events reported will be listed for individual subjects showing both verbatim and preferred terms. All adverse events that occurred prior to the initiation of study treatment will be excluded from the tables but will be included in the listings.

Missing onset dates will be imputed as previously outlined in [Section 4.1.12](#) as required to determine treatment-emergent events.

### **5.15.2. Medications and Non-Drug Therapy/Procedures**

Prior medications, concomitant medications, and medications taken post last dose of IMP will be coded using the World Health Organization (WHO) drug dictionary (WHODrug) (Version: Global B3 September 2023 or later). Prior medications, concomitant medications and medications taken post last dose of IMP will be summarized by treatment group, frequency of drug classification, and generic drug name. All medications will be presented in a data listing.

Prior non-drug therapy/procedures, concomitant non-drug therapy and procedures, and non-drug therapy/procedures taken post last dose of IMP will be coded using MedDRA Version 26.0 or higher. Concomitant non-drug therapy/procedures and non-drug therapy/procedures taken post last dose of IMP will be summarized by treatment group, frequency of system organ class and preferred term. All non-drug therapy/procedures will be presented in a data listing.

### **5.15.3. Clinical Laboratory Assessments**

Descriptive summaries of selective (quantitative) clinical laboratory results and change from baseline will be presented by study visit. Additionally, for hematology, blood chemistry, coagulation, and urinalysis parameters, toxicity grade will be determined for laboratory tests with toxicity grade specified in [Section 9.3](#). Shifts from baseline to greatest (worst) post-baseline laboratory grade will be presented. For parameters not graded as described above, laboratory values outside the normal range for each systematically collected hematology, blood chemistry, and urinalysis parameters defined in Protocol Section 10.2 will be identified using shift tables. Each subject's hematology, blood chemistry, and quantitative urinalysis values will be flagged as "low" (below the lower limit of normal/LLN), "normal" (within the normal range), or "high" (above the upper limit of normal/ULN) relative to the normal ranges of the central laboratory. Each subject's qualitative urinalysis values will be flagged as "normal" or "abnormal". Shifts from baseline to high/normal/low status for the hematology, blood chemistry, and urinalysis parameters will be presented to for the maximum post-baseline value and the minimum

post-baseline value for each laboratory test. Shifts from baseline to normal/abnormal status for urinalysis parameters will be presented to the maximum post-baseline value and the minimum post-baseline value for each laboratory test.

The number and percentage of subjects who have post-baseline elevations in transaminases (alanine aminotransferase [ALT] or aspartate aminotransferase [AST]) or bilirubin abnormalities in relation to fold above the upper limit of normal will be summarized according to the Food and Drug Administration's Premarketing Clinical Evaluation on Drug-Induced Liver Injury Guidance for Industry ([FDA 2009](#)). Abnormal hepatic laboratory values will be categorized and evaluated for any occurrence among all post-baseline assessments. [REDACTED]

[REDACTED] Within each laboratory parameter grouping, a subject may be counted once per elevation criteria using the worst-case result. That is, a subject with a worst-case ALT elevation  $> 5 \times$  the ULN would be counted once in the ALT  $> 3 \times$  ULN category and once in the ALT  $> 5 \times$  ULN category, regardless of how many ALT elevations the subject had that met the  $> 5 \times$  ULN and  $> 3 \times$  ULN elevation criteria.

- ALT and/or AST  $> 3 \times$  ULN and total bilirubin  $> 1.5$  or  $2 \times$  ULN at the same visit
- ALT and/or AST  $> 3 \times$  ULN and alkaline phosphatase (ALP)  $< 2 \times$  ULN and total bilirubin  $> 1.5$  or  $2 \times$  ULN at the same visit
- AST  $> 3, 5, 10, 20 \times$  ULN
- ALT  $> 3, 5, 10, 20 \times$  ULN
- Total bilirubin  $> 1.5, 2 \times$  ULN
- ALP  $> 1.5 \times$  ULN,  $>$  ULN to  $2.5 \times$  ULN,  $> 2.5$  to  $5 \times$  ULN,  $> 5$  to  $20 \times$  ULN,  $> 20 \times$  ULN

In addition, an eDISH plot, a shift plot showing liver safety panel tests over time (baseline vs. post-baseline), and distribution plots of ALT, AST, ALP, and bilirubin over time will be produced to aid identification of any potential cases ([Merz M. et. al. 2014](#)). The plots to be included are the scatter plot of maximum transaminase versus maximum bilirubin, the liver test safety panel over time, and the distribution of ALT by time. The distribution plots for AST, ALP, and bilirubin will use the same format as used for ALT.

The number and percentage of subjects who have glucose and lipid abnormalities will be summarized. The criteria are defined as follows:

- Glucose
  - Normal ( $< 100$  mg/dL) to High ( $\geq 126$  mg/dL)
  - Borderline ( $\geq 100$  mg/dL and  $< 126$  mg/dL) to High ( $\geq 126$  mg/dL)
- Triglycerides
  - Increase by  $\geq 50$  mg/dL
  - Normal ( $< 150$  mg/dL) to High ( $\geq 200$  mg/dL)
  - Borderline ( $\geq 150$  mg/dL and  $< 200$  mg/dL) to High ( $\geq 200$  mg/dL)

- Total Cholesterol
  - Increase by  $\geq 40$  mg/dL
  - Normal ( $< 200$  mg/dL) to High ( $\geq 240$  mg/dL)
  - Borderline ( $\geq 200$  mg/dL and  $< 240$  mg/dL) to High ( $\geq 240$  mg/dL)
- LDL Cholesterol
  - Increase by  $\geq 30$  mg/dL
  - Normal ( $< 100$  mg/dL) to High ( $\geq 160$  mg/dL)
  - Borderline ( $\geq 100$  mg/dL and  $< 160$  mg/dL) to High ( $\geq 160$  mg/dL)
- HDL Cholesterol
  - Normal ( $\geq 40$  mg/dL) to Low ( $< 40$  mg/dL)

The “Normal” and “Borderline” criteria refer to the value at baseline. The “High” and “Low” criteria refer to the post-baseline value. The “Increase” criteria refer to an increase from baseline to the post-baseline value. Within each laboratory parameter grouping, a subject may be counted once per criteria. Subjects will only be included who meet the baseline criteria and have at least one post-baseline value for the parameter.

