1.3 Schedule of Assessments

Table 1 Schedule of Assessments

Trial Periods/Phases	Screening Period ^{a,b,c}	Treatment Period										Follow-up ^d	
		-2 to -1	-	1	2	3 ^e	-	4	5	6 ^f	ET ^g		
Week	-2 to -1	-	-	1	2	3 ^e	-	4	5	6 ^f	ET ^g	10	
Day	-15 to -1	1/ Baseline ^h	4	7±2	14±2	21±2	24	28±2	35±2	42±2	45±2	NA	73±3
Entrance and History													
Informed consent	X												
Inclusion/exclusion criteria	X	X ⁱ											
Medical and psychiatric history ^j	←-----→												
MINI	X												
Demography	X												
History of drug and alcohol use	X												
Smoking history	X	X											
Review of birth control methods	X												
Breathalyzer test for alcohol ^k	X												
SARS-CoV-2 testing ^c	X												
Randomization		X											
Efficacy/Health Economics Assessments^l													
PANSS	X	X		X	X	X		X	X	X		X	
CGI-S	X	X		X	X	X		X	X	X		X	
CGI-I ^m						X				X		X	

Trial Periods/Phases	Screening Period ^{a,b,c}	Treatment Period										Follow-up ^d
		-2 to -1	-	1	2	3 ^e	-	4	5	6 ^f	ET ^g	
Week	-2 to -1	-	-	1	2	3 ^e	-	4	5	6 ^f	ET ^g	10
Day	-15 to -1	1/ Baseline ^h	4	7±2	14±2	21±2	24	28±2	35±2	42±2	45±2	NA
BACS		X								X	X	
SF-6D		X								X	X	
Safety Assessments												
Physical/neurological examination ⁱ	X										X	X
Limited physical examination ^o		X										
Height (Screening only) and weight	X	X				X					X	X
ECG ^p	X	X		X	X	X		X	X		X	X
Heart rate and blood pressure (including orthostatic) ^q	X	X		X	X	X		X	X		X	X
Respiratory rate and temperature	X	X		X	X	X		X	X		X	X
C-SSRS ^r	X	X		X	X	X		X	X		X	X
EPS (SAS, AIMS, BARS) ^s	X	X				X					X	X
Prior/concomitant treatments ^t	←-----→											
Adverse event monitoring ^u		←-----→										

Trial Periods/Phases	Screening Period ^{a,b,c}	Treatment Period										Follow-up ^d	
		-	-	1	2	3 ^e	-	4	5	6 ^f	ET ^g		
Week	-2 to -1	-	-	1	2	3 ^e	-	4	5	6 ^f	ET ^g	10	
Day	-15 to -1	1/ Baseline ^h	4	7±2	14±2	21±2	24	28±2	35±2	42±2	45±2	NA	73±3
Laboratory													
Blood for safety laboratory sample	X	X				X					X	X	
Urine for safety laboratory	X	X				X					X	X	
Prolactin level ^v		X									X	X	
Serum pregnancy test ^w	X												
Urine pregnancy test ^w		X									X	X	
Urine drug screen ^x	X	X											
Hepatitis B, C, HIV	X												
PK blood sample			X ^y			X ^z					X ^{aa}		
Blood sample for future biospecimen research ^{bb}		X											
Other													
Daily morning dose of IMP			←-----→										

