5.3 Lifestyle Considerations

5.3.1 Meals and Dietary Restrictions

Participants should fast for at least 8 hours prior to screening safety laboratory evaluations, if at all possible. If this is not possible, nonfasting screening laboratory evaluations may be obtained for eligibility determination. Participants must fast for a minimum of 8 hours prior to baseline and Week 6 safety laboratory assessments and should avoid consuming high-fat meals for 8 hours prior to any other safety laboratory assessments.

Participants should refrain from eating or drinking food/food products which are strong/moderate inhibitors of cytochrome P450 3A4 (including but not limited to grapefruit, grapefruit juice, or grapefruit-related citrus fruits/juices [eg, Seville oranges, pomelos]) from 7 days prior to dosing through Week 6/ET.

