10.2 Clinical Laboratory Tests

Protocol-required tests detailed in [Table 7](#) will be performed by a central laboratory, with the exception of those specified to be done locally in the Operations Manual.

Protocol-specific requirements for inclusion or exclusion of participants are detailed in [Section 5](#).

Additional tests may be performed at any time during the trial as determined necessary by the investigator or required by local regulations.

Serology (screening for human immunodeficiency virus, hepatitis B virus, hepatitis C virus) will be done at Screening.

Serum/urine pregnancy tests are required for all women of childbearing potential at the time points indicated in the Schedule of Assessments; however, pregnancy tests can be done anytime during the trial at the investigator's discretion.

Participants must have SARS-CoV-2 testing done with a negative test result prior to admission to the inpatient facility, refer to site procedures for additional details on

testing. Additional SARS-CoV-2 testing may be performed after admission per the investigator's discretion.

Table 7 Protocol-Required Safety Laboratory Tests

Laboratory Assessments	Parameters	
Hematology	Platelet count RBC count Hemoglobin Hematocrit Prothrombin time and INR MCH MCHC MCV	WBC count with differential (absolute and %): 
 • Neutrophils • Lymphocytes • Monocytes • Eosinophils • Basophils
Chemistry	BUN Creatinine Glucose Albumin Cholesterol (total, HDL, LDL) Triglycerides Uric acid Potassium Sodium Calcium Bicarbonate Chloride Magnesium Phosphorus	ALT AST Alkaline phosphatase GGT CPK Total bilirubin and direct bilirubin Total protein Glycosylated hemoglobin
Routine Urinalysis	Specific gravity pH, glucose, protein, blood, ketones, bilirubin, urobilinogen, nitrite, leukocyte esterase by dipstick	
Additional Required Protocol-specific Tests	Serum/urine pregnancy test (as needed in women of childbearing potential) CPK reflex for isoenzymes if CPK $>3 \times$ ULN; serum and urine myoglobin collected if CPK $>5 \times$ ULN Prolactin	
Other Screening Tests	A confirmatory FSH is required for post-menopausal women Breathalyzer test for alcohol and urine drug screen Serology (HIV, HBsAg, HBcAb, hepatitis C antibody) SARS-CoV-2 testing (Additional testing may be done at investigator discretion) Thyroid-stimulating hormone with reflex to free T4 if abnormal	

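### SAP 5.15.3 sets no visit or fasting condition for glucose and triglyceride shifts, so a possibly fed Week 3 value can be counted against a fasted baseline

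*SAP*

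**What the plan says.** Protocol 5.3.1 sets different preparation rules for different draws:

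- Baseline and Week 6: "Participants must fast for a minimum of 8 hours prior to baseline and Week 6 safety laboratory assessments".
- Screening: a fast is preferred, but "nonfasting screening laboratory evaluations may be obtained for eligibility determination".
- Every other draw: participants "should avoid consuming high-fat meals for 8 hours prior to any other safety laboratory assessments".

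In the Schedule of Assessments (Protocol 1.3), the row "Blood for safety laboratory sample" is marked at Screening, Baseline, Week 3, Week 6 (Day 45) and early termination (ET). Week 3 is the only scheduled on-treatment draw before Week 6. Protocol 10.2 puts glucose and triglycerides in the chemistry panel, so both are measured at Week 3.

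SAP 5.15.3 states: "The number and percentage of subjects who have glucose and lipid abnormalities will be summarized". The criteria at issue are:

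- glucose moving to 126 mg/dL or more, from below 100 or from 100 to below 126;
- triglycerides moving to 200 mg/dL or more, from below 150 or from 150 to below 200;
- triglycerides rising by 50 mg/dL or more.

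Two rules follow: "Within each laboratory parameter grouping, a subject may be counted once per criteria", and "Subjects will only be included who meet the baseline criteria and have at least one post-baseline value for the parameter". Neither names a visit or a fasting state, and the SAP text has no fasting flag.

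**The concern.** Glucose and triglycerides depend on recent food intake, and the protocol recognises this by making the fast mandatory at Baseline and Week 6. If the abnormality table pools all later samples, some of its shifts may reflect a meal before the Week 3 draw rather than a change in metabolic state.

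Metabolic parameters are part of a stated safety endpoint (Protocol section 3; SAP section 2). Protocol 2.2.1 also describes metabolic effects as a drawback of existing atypical agents, so readers are likely to look to this table for a contrast. Meal-driven counts would overstate incidence in each arm and make a true drug-placebo difference harder to see.

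**Working it through.** **Which samples can enter the table**

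| Draw | Preparation in Protocol 5.3.1 | Admitted by SAP 5.15.3? |
|---|---|---|
| Baseline | 8-hour fast mandatory | Reference value |
| Week 3 | Avoid high-fat meals only | Not excluded |
| Week 6 (Day 45) | 8-hour fast mandatory | Yes |
| ET | No explicit fasting rule | Not excluded |
| Unscheduled | Avoid high-fat meals only | Not excluded |

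Three related rules in the SAP do not close the gap:

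- SAP Table 2 maps ET and unscheduled chemistry values to Week 3 on study days 2 to 32 and to Week 6 from day 33. A value labelled Week 6 therefore need not come from the scheduled fasted draw.
- SAP 4.2 prefers the scheduled value within a window for summary presentations. That may keep out some unscheduled values, but it does not remove Week 3.
- SAP 4.1.6 falls back to the last earlier value if there is no predose Day 1 value. That can be a nonfasting Screening sample, so the baseline itself is not always fasted.

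**Size**

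The plan gives no abnormality rate, so there is no figure to reproduce. The rates below are assumptions.

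- f = true fasted shift rate: 2% on placebo, 5% on active.
- m = probability that a Week 3 value crosses the cut-off because of a meal, equal in all arms and independent of f: 5%, 10% or 20%.
- Counted rate = 1 − (1 − f)(1 − m).
- Difference = (f_active − f_placebo)(1 − m).
- Standard error of the difference = √[(p0(1 − p0) + p1(1 − p1))/n], where p0 and p1 are the counted rates. I take n = 124 per arm, the planned number randomized. This is an upper bound, because the table needs a qualifying baseline and a later value.

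Example at m = 5%: placebo 1 − 0.98 × 0.95 = 6.9%; active 1 − 0.95 × 0.95 = 9.75%; difference 3.0 × 0.95 = 2.85 points.

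| m | Placebo | Active | Difference (points) | Ratio | SE (points) |
|---|---|---|---|---|---|
| 0 | 2.0% | 5.0% | 3.0 | 2.50 | 2.3 |
| 5% | 6.9% | 9.8% | 2.85 | 1.41 | 3.5 |
| 10% | 11.8% | 14.5% | 2.7 | 1.23 | 4.3 |
| 20% | 21.6% | 24.0% | 2.4 | 1.11 | 5.3 |

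The difference keeps a fraction 1 − m of its true value (95%, 90% and 80%). The larger effects are on the incidence in each arm and on precision. Other assumed rates give the same pattern: for 3% versus 10% and m = 20%, the counted rates are 22.4% and 28.0%, and the difference falls from 7.0 to 5.6 points.

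**The case against.** The strongest reply is that the text proves less than it seems to.

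- **Fed status.** A reader might infer that Week 3 samples are fed. The protocol only omits the requirement to fast, and some samples may well be fasted. Avoiding high-fat meals should also lessen the triglyceride effect, though it does not address glucose. What stands is that the table cannot tell fed from fasted samples.
- **Record selection.** A reader might infer that the SAP prescribes counting any post-baseline sample. It does not say so. The sentence on inclusion decides who is in the table, not which record is used. For the hepatic criteria the same section does state that any occurrence across all post-baseline assessments counts, and here it does not. Any-visit counting is still the natural reading, and counting each subject once per criterion suggests that several values may qualify. The SAP should name the eligible records.
- **Bias between arms.** A reader might infer a bias for or against the drug. The same rule applies to all randomized, blinded arms, so the mismatch does not by itself favour either side.
- **Magnitude.** The fall in the ratio from 2.50 to 1.11 looks dramatic, but it comes largely from the choice of scale and from assumed rates. The SAP plans counts and percentages for this table, with no ratio and no test.
- **Other outputs.** By-visit summaries of selected laboratory results may show Week 3 and Week 6 separately, glycosylated hemoglobin is in the panel, and SAP 9.3 grades hyperglycemia only above 200 mg/dL. These help, but they do not separate the abnormality counts. The worst-grade triglyceride shift, where Grade 1 starts at 150 mg/dL, has the same mix.

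A further fair point is that limiting the table to Week 6 would lose early leavers, for whom Week 3 may be the only on-treatment value. The fix has to allow for that.

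**Conclusion.** The point holds as a gap between the protocol's fasting rule and the SAP's abnormality table. Under the natural reading of SAP 5.15.3, a possibly fed Week 3 value, or an ET or unscheduled value for which no fast is explicitly required, can be counted as a glucose or triglyceride abnormality against a fasted baseline.

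The expected result is higher percentages in every arm and a less clear contrast with placebo. The size is unknown. Under the assumptions above, counted rates could be several times the true ones while the absolute difference shrinks by only 5% to 20%. Those figures rest on invented shift rates, equal meal effects across arms, and independence of meal-driven and true shifts.

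The table is a descriptive safety summary, and the primary and key secondary efficacy analyses are untouched. The change is worth making because it is cheap and uses data already collected.

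**What to change.** In SAP 5.15.3:

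1. State which post-baseline records are eligible for the glucose and triglyceride criteria.
2. Present the shift and increase criteria by visit. Make the scheduled Week 6 draw against Baseline the main fasted comparison, and show Week 3 separately with the label 'fasting not required'.
3. Admit ET and unscheduled values to the fasted comparison only if fasting status was recorded; otherwise show them separately. This should override the Table 2 mapping of ET values from day 33 to Week 6. Flag any baseline taken from a Screening sample.
4. Keep an any-post-baseline row, so that early leavers still contribute.
5. Apply the same split, or a footnote, to the worst-grade triglyceride shift.

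The cost is SAP wording and one extra table. The fasted comparison will include fewer participants, mainly early discontinuers. Protocol 9.5 expects about 25% discontinuation, which is about 31 of 124 per arm (0.25 × 124). No part of the documents shows that fasting status is recorded, so item 3 may in practice mean showing ET and unscheduled values separately. No new sampling is needed.
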